4.5 Duration of Study Participation

Each subject will be enrolled in the study for approximately 25 months from the initial screening visit until the last follow-up visit at 24 months post intervention.

4.6 Total Number of Participants and Sites

Data from 40 participant will be required and the study would accrue 50 patients to account for an attrition rate of 20%. Withdrawn subjects and subjects who did not completed at least the 6-month visit can be replaced.

The study will be conducted only at NYULH Hospitals. No subjects will be enrolled at external national or international sites.

4.7 Participant Withdrawal or Termination

4.7.1 Reasons for Withdrawal or Termination

Participants are free to withdraw from participation in the study at any time upon request. An investigator may terminate participation in the study if:

Participation of a patient in this clinical study may be discontinued for any of the following reasons:

- The patient withdraws consent or requests discontinuation from the study for any reason;
- Occurrence of any medical condition or circumstance that exposes the patient to substantial risk and/or does not allow the patient to adhere to the requirements of the protocol;
- Any AE, clinically significant adverse event, severe laboratory abnormality, intercurrent illness, or other medical condition that indicates to the investigator that continued participation is not in the best interest of the patient;
- Pregnancy during study period;
- At the discretion of the study PI if patient fails to comply with protocol requirements or study-related procedures, including failure to attend any of the study visits within the protocol-defined window;
- Termination of the study by the Sponsor, the regulatory authority, FDA, or IRB.
- The participant meets an exclusion criterion (either newly developed or not previously recognized) that precludes further study participation

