4.2 Exclusion Criteria

An individual who meets any of the following criteria will be excluded from participation in this study:

1. Active systemic or local knee[#] infection
2. Active malignancy
3. Life expectancy less than 6 months
4. Prior ipsilateral knee arthroscopic surgery or repeat TKA (within 9 months of screening)
5. Ipsilateral knee intra-articular injection in the last 3 months
6. Rheumatoid arthritis, spondyloarthropathies, crystal disease, gout, pseudogout, or lupus
7. Pregnant during the study period
8. Renal dysfunction as defined by serum creatinine >1.6 dl/mg or eGFR <60 on blood tests obtained within 30 days of procedure
9. Body weight greater than 200 Kg
10. Known history of severe contrast allergy to iodinated contrast resulting in anaphylaxis
11. Known significant arterial atherosclerosis that would limit selective angiography and/or lower extremity symptoms thought to be secondary to arterial vascular disease (eg claudication, ischemic rest pain)
12. Known avascular necrosis in the target knee
13. Complications of TKA such as suspected or confirmed early loosening, ligamentous instability, reflex sympathetic dystrophy, polyethylene wear with or without particle disease (osteolysis), patellofemoral mal-tracking, referred hip and low back pain, and large effusions** (with or without hemarthrosis) on available imaging studies such as knee radiographs, computed tomography scans, and / or the MRA performed for the study purposes.
14. Patient is enrolled in a different trial for treatment of knee pain post total knee arthroplasty (ipsilateral knee)

using Musculoskeletal Infection Society (MSIS) criteria for diagnosis of prosthetic joint infection

2011 Musculoskeletal Infection Society (MSIS) criteria ^[1]	
PJI is present when 1 major criteria exist or 4 out of 6 minor criteria exist	
Major criteria:	
	
 ■ 2 positive periprosthetic cultures with phenotypically identical organisms ■ A sinus tract communicating with the joint
Minor criteria:	
	
 ■ Elevated CRP and ESR ■ Elevated synovial fluid WBC count or ++ change on leukocyte esterase test strip ■ Elevated synovial fluid PMN% ■ Presence of purulence in the affected joint ■ Positive histologic analysis of periprosthetic tissue ■ A single positive culture

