4.7.2 Handling of Participant Withdrawals or Termination

If a patient withdraws prematurely from the study due to the above criteria or any other reason, study staff should make every effort to complete the full panel of assessments scheduled for the follow-up visits. The reason for patient withdrawal must be documented. In the case of loss of follow-up, attempts to contact the patient will be made and documented in the patient's medical records. Every effort will be made to undertake protocol-specified safety follow-up procedures to capture AEs, serious adverse events (SAEs), and unanticipated problems (UPs). Withdrawn patients can be replaced (do not count toward the protocol-defined sample size).

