5.1.7 Duration of Therapy

Treatment will be completed during one interventional session (visit 3, day 0).

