7.4.4 Reporting of Pregnancy

If the subject participating in the study is found to be pregnant during the study period, participant will immediately be withdrawn from the study and IRB will be informed.

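### Patients already treated can be discontinued for a missed window or a newly met exclusion criterion and then replaced, which can inflate the single-arm success rate

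*Combined protocol and SAP*

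**What the plan says.** - **Treatment.** Section 5.1.7: "Treatment will be completed during one interventional session", on Day 0. Section 3.1 describes a single-arm, open-label study, and Section 7.5 identifies the sponsor as the principal investigator (PI).
- **Discontinuation.** Section 4.7.1 allows it at the PI's discretion for non-compliance, including "failure to attend any of the study visits within the protocol-defined window". A further ground is: "The participant meets an exclusion criterion (either newly developed or not previously recognized) that precludes further study participation". Nothing says which criteria preclude participation once the only treatment session is over.
- **Overlap with harms.** Section 4.2 excludes active knee infection and "Known avascular necrosis in the target knee". Section 1.4.1 lists joint infection and osteonecrosis among the rare adverse events.
- **Replacement.** Section 4.7.2: "Withdrawn patients can be replaced (do not count toward the protocol-defined sample size". Section 4.6 extends replacement to anyone who did not complete the 6-month visit. Neither section limits it to patients who were not treated.
- **Analysis.** Section 9.3 includes patients who received the device and completed at least the 3-month visit. It has no rule for a missing 6-month outcome and does not say whether replaced patients stay in. Section 9.1 says there will be no formal SAP.

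**The concern.** With a single session on Day 0, no later exposure remains to be stopped. A discontinuation after that day acts only on follow-up, including whether a 6-month value exists. Section 4.7.1 does not separate stopping study procedures from stopping data collection.

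The two grounds at issue can be related to outcome. A patient who is doing badly may be more likely to miss a window, and some exclusion criteria coincide with listed harms. The decision rests with a sponsor-investigator who knows how the patient is doing. Under Section 9.4.5, that investigator may also have seen results from the first 10 completers.

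The primary result is one proportion with no control arm, so selective loss has nothing to show up against. If failures leave and are replaced until 40 patients have a 6-month visit, the observed rate overstates the rate among those treated. Redefining the analysis set alone would not cure this, because Sections 4.6 and 4.7 would still decide who has a 6-month value.

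**Working it through.** **The plan's own figures.** Section 9.5 gives H0: rate ≤ 0.50, HA: rate ≥ 0.75, a 5% level, 40 six-month completers and 20% attrition.

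- Enrolment: 40 / (1 − 0.20) = 50. This reproduces.
- Power: the stated 80.4% at a realized level of 0.047 does not reproduce at n = 40. The one-sided exact binomial test at n = 40 rejects at 26 or more successes, with level 0.0403 and power 94.6%. The stated pair matches n = 23 with 16 or more (0.0466 and 80.4%). This is a separate matter. It matters here only because the plan states no cutoff for 40 patients, so one has to be assumed.

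**Assumed cutoffs.**
- 26/40 is the exact one-sided 5% boundary against 0.50.
- 30/40 is an observed 75%, one reading of the success statement in Section 9.2.

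**Model.** Let p be the true success rate, w the share of failures withdrawn and replaced, and v the share of successes withdrawn and replaced, with recruitment until 40 are evaluable. The documents give neither w nor v; both are assumptions.

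Apparent rate = p(1 − v) / [p(1 − v) + (1 − p)(1 − w)]

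False-success chance = P(X ≥ c), where X is binomial with n = 40 and the apparent rate.

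**Only failures replaced (p = 0.50, v = 0).** The apparent rate becomes 0.5 / (1 − 0.5w).

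| w | Apparent rate | Patients treated to reach 40 | Failures replaced | c = 26 | c = 30 |
|---|---|---|---|---|---|
| 0 | 50.0% | 40.0 | 0 | 4.0% | 0.1% |
| 10% | 52.6% | 42.1 | 2.1 | 7.9% | 0.3% |
| 20% | 55.6% | 44.4 | 4.4 | 14.8% | 0.9% |
| 40% | 62.5% | 50.0 | 10.0 | 44.1% | 6.8% |

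Patients treated = 40 / (1 − 0.5w). Failures replaced = 0.5w × that number. The last row uses the whole planned attrition of 10 out of 50 and makes every one of them a failure, so it is an upper extreme.

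**Successes lost as well.**
- w = 20%, v = 10%: apparent rate = 0.45 / (0.45 + 0.40) = 52.9%. The false-success chance at 26/40 is 8.5%.
- w = v: the apparent rate is 50%, and the chance stays at 4.0% (26/40) or 0.1% (30/40).

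**Effect on a reported result.** If 30 of 40 evaluable patients succeed and 10 treated patients were replaced, the report reads 30/40 = 75%. With all treated patients in the denominator and those 10 counted as non-successes, it reads 30/50 = 60%.

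**The case against.** Discontinuation is permitted, not required, and the exclusion-criterion ground is qualified. Section 4.7.2 asks staff to make every effort to complete the scheduled assessments, and Section 6.3.5 provides an early termination visit with questionnaires and adverse event recording. The remark that withdrawn patients do not count can be read as an enrolment tally, since Section 9.3 still admits a treated patient with a 3-month visit. Missed windows may affect responders and non-responders alike. All of this stands. It makes the bias possible rather than certain, but it does not say how a replaced patient enters the 6-month rate.

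Three stronger readings are tempting and are not supported:

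- **That any adverse event is a ground for removal.** Section 4.7.1 ties that ground to the investigator's judgement that continuing is not in the patient's best interest.
- **That a knee injection is a withdrawal route.** The criterion "Ipsilateral knee intra-articular injection in the last 3 months" is worded as a look-back at entry. Section 6.1.1 expects injections to be recorded during follow-up, and Section 6.6 prohibits no treatments. An injection increase defeats success only in the Protocol Summary; Sections 2.1 and 3.1 mention analgesics alone.
- **That harms are generally understated.** An infection or osteonecrosis that prompts withdrawal would already be a recorded event, and replacing the patient does not delete it. Section 7.3 requires all on-study events to be documented, continues recording for 7 days (non-serious) or 30 days (serious) after participation ends, and follows unresolved events.

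**Conclusion.** The point holds for the primary success rate. Taken together, Sections 4.6, 4.7.1 and 4.7.2 let treated patients be discontinued on grounds that may track outcome and then be replaced, while Section 9.3 leaves their place in the primary rate undefined. This is a stated rule that permits bias, not merely an omission.

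The direction is upward if failures are lost more often than successes. The size cannot be derived from the documents. At a true rate of 50%, with only failures replaced and w between 10% and 40%, the false-success chance is 7.9% to 44.1% at 26/40 (4.0% without replacement) and 0.3% to 6.8% at 30/40 (0.1% without). It does not rise when both groups are lost equally. These figures rest on assumed withdrawal shares and cutoffs. They should be read as showing sensitivity, not as a forecast.

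**What to change.** 1. **Sections 4.6 and 4.7.2:** limit replacement to patients who did not receive the device. Any extra enrolment adds to the treated patients in the primary denominator and does not substitute for them.
2. **Section 4.7.1:** state that after Day 0 a missed window or a newly met exclusion criterion does not by itself end collection of outcome and safety data. Clinical decisions about study procedures, and the consent, best-interest and pregnancy rules, stay as they are.
3. **Section 9.3:** reconcile with 4.6 and 4.7.2. Keep all treated patients in the primary analysis, count those without a 6-month outcome as non-successes, and add a completers-only sensitivity analysis.
4. **Separately:** reconcile the Protocol Summary with Sections 2.1 and 3.1 on whether injections are part of the success definition.

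The cost is protocol wording, with no visits beyond those scheduled. The reported rate may be lower, because outcome-neutral loss also counts against the treatment: a true 75% with 20% missing at random would read 0.75 × 0.80 = 60%. The completers-only analysis shows how much of any drop comes from missing values.

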4.7.2 Handling of Participant Withdrawals or Termination

If a patient withdraws prematurely from the study due to the above criteria or any other reason, study staff should make every effort to complete the full panel of assessments scheduled for the follow-up visits. The reason for patient withdrawal must be documented. In the case of loss of follow-up, attempts to contact the patient will be made and documented in the patient's medical records. Every effort will be made to undertake protocol-specified safety follow-up procedures to capture AEs, serious adverse events (SAEs), and unanticipated problems (UPs). Withdrawn patients can be replaced (do not count toward the protocol-defined sample size).

4.8 Premature Termination or Suspension of Study

This study may be temporarily suspended or prematurely terminated if there is sufficient reasonable cause. Written notification, documenting the reason for study suspension or termination, will be provided by the suspending or terminating party to investigator, funding agency, the IDE sponsor and regulatory authorities. If the study is

prematurely terminated or suspended, the PI will promptly inform the IRB and will provide the reason(s) for the termination or suspension.

Circumstances that may warrant termination or suspension include, but are not limited to:

- Determination of unexpected, significant, or unacceptable risk to participants
- Insufficient compliance to protocol requirements
- Data that are not sufficiently complete and/or evaluable

Study may resume once concerns about safety, protocol compliance, data quality are addressed and satisfy the sponsor, IRB and/or FDA.

5 Study Agent (Study device) and Procedural Intervention

5.1 Study Agent(s) and Control Description

Embozene™ Microspheres are spherical, tightly calibrated, biocompatible, nonresorbable, hydrogel microspheres coated with an inorganic perfluorinated polymer (Polyzene™-F). The microspheres are intended to occlude vasculature for the purpose of blocking blood flow to a target tissue. They are available in prefilled syringes in a range of sizes suitable for embolic therapy. The microspheres are compressible to enable smooth delivery through the indicated delivery catheter and color-coded by size to allow for easy identification. **100 µm microsphere will be used and are supplied in prefilled syringes.**

Embozene Microspheres are intended for embolization of arteriovenous malformations and hypervasculair tumors, including uterine fibroids and hepatoma, and for embolization of prostatic arteries for symptomatic benign prostatic hyperplasia. This device is not intended for neurovascular use. The device is FDA approved for above indications (FDA approved for treatment of BPH; FDA approval 510(K) # K180102; 510(k) premarket notification of intent to market the device FDA 510(k) # K141209)

There are no known chemical interactions between Embozene Microspheres and pharmaceuticals.

IDE for the purpose of this study was obtained from the FDA.

5.1.1 Acquisition

Embozene™ Microspheres will obtained from the manufacturer.

5.1.2 Formulation, Appearance, Packaging, and Labeling

Embozene Microspheres are supplied in a 20 ml syringe prefilled with 2 ml of product suspended in a non-pyrogenic, sterile transport solution of physiological saline. The total volume of Embozene Microspheres including transport solution is approximately 7 ml. Prefilled syringes of Embozene Microspheres are packaged in a sterile, sealed tray with a peel-away lid. The label indicates the specific size of the microspheres contained in the syringe. **100 µm microsphere will be used and are supplied in prefilled syringes.**

5.1.3 Product Storage and Stability

As per manufacturer's instructions specified in the DFU, the device should be stored in a cool, dry, dark place. Product must be used prior to expiration date on label. The investigational device will be stored in a secure locked cabinet in the interventional radiology storage area (Tisch hospital, 2nd floor) and only the PI, investigators, and research coordinator will have access to the lock.

5.1.4 Preparation

Embozene Microspheres are supplied in a 20 ml syringe prefilled with 2 ml of product suspended in a non-pyrogenic, sterile transport solution of physiological saline. The total volume of Embozene Microspheres including transport solution is approximately 7 ml.

Prior to embolization, the transport solution will be eliminated from the syringe. An embolic mixture will be prepared by adding 9 cc saline + 9 cc iodinated contrast added to the 2 cc of product (Embozene Microspheres) for a total of 20 cc embolic mixture.

5.1.5 Dosing and Administration

The embolic mixture will be injected in small increments until embolization end-point (pruning of distal vasculature) in the target artery is reached (0.5-1 cc embolic mixture injected over 2 minutes, followed by 1 cc saline delivered slowly, then 3 cc saline flush).

5.1.6 Route of Administration

The embolic mixture will be injected in small increments in the target geniculate artery(ies) after selective catheterization of the target vessel(s) using a microcatheter to reach distal arteries while avoiding branches that do not feed abnormal vessels.

5.1.7 Duration of Therapy

Treatment will be completed during one interventional session (visit 3, day 0).

5.2 Study Procedural Intervention(s) Description

On the day of the procedure (visit 3, day 0), the subjects will be given the choice of receiving intravenous anxiolytic and analgesic medication (moderate sedation) during procedure or proceeding with local anesthetic only. Arterial access site will be prepped and draped using sterile technique. Femoral artery access will be obtained with a micropuncture needle set and a vascular sheath or a guiding catheter will be placed in the femoral artery to maintain vascular access. A guiding catheter will be placed and lower extremity digital subtraction angiography (DSA) will be performed to depict the genicular arteries in all patients. Angiography will be performed to identify abnormal knee neovasculation arising from one or more of geniculate arterial branches.

After localizing the abnormal neovessels (abnormal vessels appear as tumor blush-type enhancement in the arterial phase, often accompanied by early venous drainage /hypervascula synovial tissue in the region of the target knee joint), a microcatheter will be inserted coaxially through the guiding catheter and selectively placed in the targeted artery(ies). If there is uncertainty about the angiographic findings, pre-embolization simulation can be performed with contrasted cone beam computed tomography (CBCT). This will allow the operators to know exactly what tissues will be receiving the microspheres. The abnormal vessels will be embolized with **100 µm Embozene™ Microspheres** solution under direct fluoroscopic visualization to prevent reflux and non-target embolization. Multiple geniculate arteries may be embolized until neovascularity is no longer seen.

The embolic mixture will be prepared by adding 9 cc of saline + 9 cc of contrast to the 2 cc Embosepheres for a total of 20 cc embolic mixture. Injection of the embolic mixture will continue in small increments until an end point of at least 'pruning' of the hypervascula synovium in the target artery(ies) (0.5-1 cc embolic mixture injected over 2 minutes, followed by 1 cc saline delivered slowly, then 3 cc saline flush). In some cases, more selective catheterization will be performed by using the microcatheter to reach distal arteries while avoiding branches that do not feed abnormal vessels. After embolization, a repeat lower extremity angiogram and contrasted CBCT (if needed) will then be performed to evaluate for success of embolization and to exclude complication. The catheter(s) and sheath will be removed, and hemostasis of the arterial access will be achieved by an FDA-approved arterial closure device or manual compression and bed rest for 2-6 h after the femoral artery sheath removal. All participants will be monitored for 2-6 hours post procedure and any adverse events will be documented and managed. If hemostasis is obtained by a vascular closure device, it is anticipated that most participants will be discharged home 2 hours post procedure. If hemostasis is obtained by manual compression, it is anticipated that most participants will be discharged home within 2-6 hours post procedure.

Disposable syringes which spherical particulate will be discarded as medical waste and packaging will be kept in a secure location and/or packaging LOT number will be documented until the study is completed. Packages will be disposed of upon completion of the study.

5.2.1 Administration of Procedural Intervention

Procedures will be performed by an IRB-approved interventional radiologist with fellowship training in Vascular and Interventional Radiology. The interventional procedure will be performed during one session (day 0) with an approximate duration of the procedure estimated between 1-4 hours. Additional 2-6 hours will be needed after hemostasis of the access femoral artery is achieved for monitoring / observation. In general, the subject will be discharged home the same day (<23 hours) unless a complication arises that requires inpatient admission or overnight observation for management of the complication.

5.2.2 Procedures for Training of Clinicians on Procedural Intervention

All proceduralists performing the intervention will be vetted and credentialed by the site PI, with the following requirements for credentialing:

- 1- Fellowship trained in vascular and interventional radiology.
- 2- Board certified by the American Board of Radiology
- 3- License to practice medicine in New York
- 4- Performed at least three GAE procedures (cases performed during training are accepted) as a primary and/or assistant operator.

Prior to site activation, all investigators will complete a study training by the site PI and sign a training log.

6 Study Procedures and Schedule

